### 12.4 Additional exploratory analysis

In addition to hypothesis testing, we will characterize the change in HPV viral load over the course of the trial using longitudinal data modeling. For each individual, we will have data on HPV viral load at weeks -2 (Screening visit), 9-10, and 15. A random effects model will be used to model the distribution of HPV viral load over time:

$$hpv_{it} = \beta_{0i} + \beta_1 t + \beta_2 t^2 + \varepsilon_{it}$$

where  $hpv_{it}$  is individual  $i$ 's HPV viral load at week  $t$ . Correlations between observations within an individual are accounted for by the random intercept (i.e. random effect) term. A quadratic model is used to account for non-linearity in the change of HPV viral load. From the fitted model, we can estimate the effect of the vaccine treatment on viral load. The plot below is based on simulated data and shows the type of result we hypothesize: a downward trend in HPV viral load that flattens as time increases. Based on the random effects model shown above, we can estimate the average response (denoted by the thick line) and better understand the association between the vaccine and response and specifically when changes in viral load tend to occur.

Lesion size will also be described using the random effects linear longitudinal model described above to look for time trends.

The secondary efficacy endpoints will be compared with analogous data obtained in a currently open cohort study, “Evaluation of Tissue and Peripheral Blood Immune Response in Women with HPV16+ Cervical Intraepithelial Lesions” (Johns Hopkins IRB# NA\_00037578). This observational cohort protocol has been open since 1999, and currently includes over 250 subjects. These subjects have the same eligibility criteria as the criteria for this trial, and are followed prospectively for the same timeframe, before undergoing standard therapeutic resection at week 15. To date, no CIN2/3 lesions have progressed to invasive disease in this timeframe, which is well within the standard of care. We will compare changes in HPV viral load and lesion size from baseline at Week 15, rates of histologic regression, and change in viral load over the 15 week window, in both cohorts.

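### Section 12.4 reads a treatment effect from a viral-load time curve that cannot separate drug from natural course, and lists a week 9-10 sample that no scheduled visit supplies

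*Combined protocol and SAP*

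**What the plan says.** Section 12.4 describes the sampling for the model as "For each individual, we will have data on HPV viral load at weeks -2 (Screening visit), 9-10, and 15". It then gives a quadratic in week with a subject-specific intercept. Two sentences interpret the fit as a drug effect: "From the fitted model, we can estimate the effect of the vaccine treatment on viral load", and a later one saying that the model helps to "better understand the association between the vaccine and response". The expected result is "a downward trend in HPV viral load that flattens as time increases".

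For lesion size the same section is more modest: "Lesion size will also be described using the random effects linear longitudinal model described above to look for time trends".

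The plan has an outside reference in two places.

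- Section 7.2 takes indicators of efficacy from a significant difference (chi-square, p below 0.1) between treated women and baseline data in a Johns Hopkins colposcopy database.
- Section 12.4 turns to an observational cohort of more than 250 women who are followed to resection at week 15: "We will compare changes in HPV viral load and lesion size from baseline at Week 15". The same sentence adds the change in viral load across the 15-week window in both groups.

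That cohort's title is "Evaluation of Tissue and Peripheral Blood Immune Response in Women with HPV16+ Cervical Intraepithelial Lesions", yet the text says "These subjects have the same eligibility criteria as the criteria for this trial". Section 9.1 of this trial admits any woman who is HPV-positive on a DNA test.

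**The concern.** A curve fitted to treated women only describes what happened to them over time. It becomes a treatment effect only if viral load would have stayed flat without the drug, and section 5.0 gives reason to doubt that. If the drug did nothing, the curve could still fall in the way 12.4 hypothesizes, and the text would report the fall as the effect of treatment. What is at stake is the conclusion about antiviral activity, which the Synopsis allows to carry into later trials when an exploratory p-value is 0.10 or less.

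The week list is a separate fault. An analyst who follows 12.4 literally would look for a middle sample that the schedule does not produce.

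**Working it through.** **1. What the model can identify.** In plain notation, load(i,t) = a(i) + b1·t + b2·t² + error. The treatment cohorts in Table 4 are 50 mg for one cycle and 200 mg for one, two or three cycles. None of these appears in the equation, and neither does an untreated group. Hence b1 and b2 are averages over regimens of (natural course + drug effect), and no feature of the fit separates the two parts.

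**2. Whether any visit gives week 9-10.** Windows from section 10.2 and Table 3:

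| Visit | Weeks covered |
|---|---|
| Screening (3 ± 2 weeks before dosing) | -5 to -1 |
| Week 2 ± 1 | 1 to 3 |
| Week 4 ± 1 | 3 to 5 |
| Week 6 ± 1 | 5 to 7 |
| Week 15 ± 1 | 14 to 16 |
| Postoperative, 4 ± 1 after a week 15 resection | 17 to 21 |
| Week 28 ± 2 | 26 to 30 |
| Week 41 ± 2 | 39 to 43 |

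None overlaps 9-10; week -2 does fall within screening. Two edge routes exist. A postoperative visit after early resection for progression at the interval visit falls at 5+3 = 8 to 7+5 = 12. A Cohort IV safety check with every allowance stacked (third cycle begun at week 5, two weeks to finish, check two weeks later) falls at 5+2+2 = 9. Neither applies to every woman.

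**3. Whether the model can still be fitted.** The mean curve has three parameters.

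- With nominal weeks -2 and 15 only, it cannot be estimated.
- With those two visits spread over their windows, it can be, but the standard error of b2 is about 4.3 times that obtained when week 6 is included (30 women).
- With screening, 6 and 15 it is estimable, with 3 - 3 = 0 degrees of freedom left to check the shape at nominal times.
- Table 3 also schedules a swab at week 0 for everyone, which leaves 4 - 3 = 1.

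**4. Size, as illustration only.** The documents give no viral clearance rate, fall or SD. Assume an inert drug; a share p of 5-25% clearing untreated; a fall d of 1-3 log10 in those who clear; and an SD of change of 0.7 log10. The mean fitted fall is p × d, from 0.05 × 1 = 0.05 to 0.25 × 3 = 0.75 log10, all of it natural course. Simulated chance of a significant fall at two-sided 0.10 (nominal 5% in that direction), 30 women:

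| p | Fitted change, 12.4 model (screening, 6, 15) | Paired t-test |
|---|---|---|
| 5% | 10-25% | 9-17% |
| 10% | 19-51% | 17-38% |
| 20-25% | 42-95% | 37-90% |

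The model's rates are higher partly because a random intercept alone understates the standard error of change. For one level of 9 women, the paired t-test of section 12.2 gives about 7% to 33% over the same values.

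**The case against.** The strongest reply is that the plan does not rely on this model for efficacy. Section 7.2 ties efficacy to a difference from outside data, and 12.4 plans a cohort comparison that covers both the week 15 change and the change across the window. That stands. A reader might infer that the plan has no untreated reference for viral load, and the documents do not support that reading. What remains is an inconsistency: the model sentences claim what the plan elsewhere reserves for an external comparison.

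That comparison also needs tidying. Section 7.2 names a database and 12.4 a cohort study, and they are not said to be the same. Chi-square does not suit a continuous measure. The HPV16 title does not match the claim of identical eligibility, and genotype matters because section 5.0 says other types regress more often.

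The second reply is that 12.4 is descriptive and exploratory in a phase I trial whose primary outcome is safety, and that it specifies no test of the fitted change. This also stands. The model rejection rates above belong to a test added for illustration. The highest of them use 20-25%, which is an HPV16 lesion regression rate and not a viral clearance rate. Thirty women is one reading of the sample size; section 12.1 gives up to 39 for escalation and 12 more for expansion.

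A reader might also infer that the model cannot be fitted, or that choice of the expansion level is badly compromised. Neither follows. The scheduled swabs make the quadratic estimable. Section 12.1 also asks for lesion clearance, words the rule as a general one, and falls back on the totality of evidence. On one reading of the lesion half (chi-square at 0.1 against 250 untreated women), both halves are met with an inert drug in about 1-6% of cases.

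**Conclusion.** The point holds in a limited form. As written, the 12.4 model shows change over time on study, averaged over four regimens and including natural course. It does not estimate a drug effect, and the two sentences that say so should go. The week 9-10 entry matches no scheduled visit, and the word vaccine does not describe this trial's drug. These conclusions come from the text and the equation and need no simulation.

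The size of any misreading cannot be taken from the documents. The 0.05 to 0.75 log10 range and the rejection rates rest on assumed inputs. The consequence is confined to what may be concluded about viral-load activity. The primary safety analysis is untouched, and any effect on level selection is minor. The correction should be made because it is cheap and removes a claim the data cannot support.

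**What to change.** 1. In 12.4, replace the listed weeks by the scheduled visits at which viral load will be assayed: at least screening, week 6 and week 15. First reconcile the sampling descriptions: section 5.0 (swabs at each vaginal exam), Table 3 (swabs at every visit, with weeks 2 and 4 by group), section 10.3 (brush specimens at entry, week 5 and week 15) and section 10.4 (viral-load specimens under colposcopy). Use actual sampling times and the log scale of 12.2.
2. Replace both effect-of-vaccine sentences by a description of change over time on study, pooled over regimens and including natural course. The lesion-size sentence in 12.4 is the model to follow.
3. State that any claim of drug effect on viral load rests on the external comparison already planned in 7.2 and 12.4, described as non-concurrent. Say which data source is meant, name a method suited to a continuous measure, reconcile the cohort's HPV16 title with the eligibility statement, and compare like genotypes.
4. Optionally, note in 12.1 that the within-subject viral-load test is against no change.

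The cost is wording and a weaker claim about activity, with no new visits or patients. The external contrast will be imprecise. Under the assumptions above and with 250 cohort women, the 90% interval half-width is 1.645 × √(0.49 + p(1-p)d²) × √(1/n + 1/250). This gives 0.41 to 0.82 log10 for a level of 9 and 0.23 to 0.47 for 30 women, and wider intervals if only HPV16-positive women can be compared. The documents do not give the cohort's viral-load sampling weeks or genotype mix.

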we and others have also reported that in this timeframe, approximately 20-25% of CIN2/3 lesions associated with HPV16 will undergo regression [63]. Lesions that are associated with HPV genotypes other than HPV16 are even more likely to regress in this timeframe [64]. Moreover, in this population, it is feasible to visualize directly, quantitate serially, and perform therapeutic resection of premalignant lesions. Based on safety and tolerability data in pediatric populations receiving intrarectal suppositories at a dose that is approximately five-fold compared to the regimen we propose in this clinical protocol, we do not expect dose-limiting toxicities with the dosage and regimen proposed in this proof-of-principle study. The [name] group has a decade of experience in the design and execution of prospective clinical protocols specific for this patient cohort, testing immunotherapeutic interventions prior to standard therapeutic resection of any residual lesions. [65, 66]. The parallel design of this trial will allow comparison of tissue-based endpoints in this cohort.

Despite the experience with active immunotherapy in other tumor models, it is still not clear what measures of immune response are relevant to lesion regression. In particular, it does not appear that classic measures of immune response, measured in the circulation, correlate at all with clinical response. Because the biology of HPV disease is extensively characterized; because there are known, quantifiable risk factors for persistence and progression of disease; because we have ready access to an immunocompetent population of patients at elevated risk for carcinoma development; and because we can directly visualize and subsequently therapeutically resect and analyze affected tissue; we are presented with an opportunity to rapidly evaluate therapeutic regimens, characterize relevant immune responses, and provide direction for future interventions, both in this disease and in other tumor models. The relatively long precursor phase in HPV disease also provides many opportunities for intervention, including, optimally, prophylaxis against the development of cancer.

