### **7.2 Secondary Outcome Measures**

Indicators of drug efficacy (see below) will be drawn from any evidence demonstrating a significant difference (by simple chi-square analysis;  $p < 0.1$ ) between treated subjects and the baseline data in the Johns Hopkins Colposcopy database

- Extent of lesion clearance (by lesion number, size, and/or area of coverage)
- Presence/absence of HPV DNA
- Regression of CIN stage by histopathology (comparison of initial biopsy to LEEP/cone excision-procured tissue).

Histologic regression will be judged as none (persistent CIN2/3 in week 15 resection specimen) or total (no CIN2/3 in resection specimen).

Virologic HPV viral load. Longitudinally obtained cervical swabs will be used to quantitate HPV viral load as a continuous variable.

Tissue sections from the diagnostic biopsy obtained as part of the screening process, and from the resection specimen obtained post-treatment will be assessed for expression of CD8 (effector T cells), CD71 (transferrin receptor), and cleaved caspase 3 (apoptotic cell death).

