## **8.0 STUDY DESIGN**

Prior to enrollment, patients referred for evaluation of an HSIL pap smear will undergo a full colposcopic evaluation, with biopsy confirmation. Clinical, histopathologic, virologic, and immunologic parameters will be assessed longitudinally in each study participant, as outlined below. The trial is a dose-escalation design, with a run-in cohort to assess the likelihood of mucosal irritation.

These serial assessments will directly parallel those obtained in the currently open CIN2/3 cohort study (JHMI JCCI# 99-08-27-04). Those patients who have measurable disease after biopsy will be eligible for study participation.

Cervical tissue specimens obtained as routine diagnostic and therapeutic specimens will be analyzed to characterize local tissue immune response. Diagnostic biopsies obtained at initial colposcopy will be used to confirm the diagnosis of CIN2/3. The initial diagnostic biopsy specimens will also be characterized in terms of type and quantitation of inflammatory cell infiltrates. Immunocytochemical techniques will be used to determine presence and numbers of macrophages, dendritic cells, T cells, B cells, and NK cells. We will also use standard staining techniques to detect cleaved caspase 3. As tissue availability permits, the specimens will also be analyzed for other immune cells. We will be comparing tissue profiles with those obtained on circulating PBLs in our study population. In the post-suppository administration, therapeutic LEEP/cone biopsy specimens, markers of local tissue immune response will be similarly characterized and quantitated. [name] will review all of the histologic slides.

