### **9.1 Subject Inclusion Criteria**

- \* Patients with high-grade cervical intraepithelial lesions (CIN2/3) confirmed by colposcopy and biopsy.
- \* Patients who have measurable disease after diagnostic biopsy.
- \* Patients who weigh  $\geq 50$  kg
- \* Patients who are HPV-positive by DNA test
- \* Patients who are age 18 or older.
- \* Patients who are able to give informed consent.
- \* Patients who are immunocompetent.
- \* Patients who are not pregnant; committed to using adequate contraception through week 15 if of childbearing age. Condom use will be encouraged.
- \* Patients who have the ability to collaborate planned follow-up

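### The external cohort in 12.4 is titled HPV16+ but said to share this trial's any-HPV eligibility; with no genotype handling, an HPV16-only cohort would tilt the histologic-regression comparison towards the drug

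*Combined protocol and SAP*

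**What the plan says.** Section 12.4 plans to set the secondary efficacy endpoints beside those of an observational cohort open since 1999 with more than 250 subjects, titled "Evaluation of Tissue and Peripheral Blood Immune Response in Women with HPV16+ Cervical Intraepithelial Lesions". The same paragraph says "These subjects have the same eligibility criteria as the criteria for this trial". The quantities to be compared include "rates of histologic regression, and change in viral load over the 15 week window, in both cohorts".

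This trial's HPV criterion (Section 9.1, repeated in the Synopsis) is "Patients who are HPV-positive by DNA test", with no genotype limit.

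Section 5.0 gives the background rate within the study window: "approximately 20-25% of CIN2/3 lesions associated with HPV16 will undergo regression". It adds: "Lesions that are associated with HPV genotypes other than HPV16 are even more likely to regress in this timeframe".

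Other sections describe an external reference differently. Section 7.2 applies a simple chi-square at p < 0.1 to "treated subjects and the baseline data in the Johns Hopkins Colposcopy database". Section 8.0 refers to a CIN2/3 cohort under a different study number. Section 9.0 says that the group's cohort and vaccine studies draw on the same population as this trial. None of these gives a genotype criterion or mix.

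Trial patients are genotyped at screening and at weeks 6, 15, 28 and 41 (Table 3; Section 10.4), but genotype has no stated role in the external comparison. The logistic model in 12.4 is fitted within the trial.

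**The concern.** If the title states the cohort's HPV criterion, the sentence on shared eligibility is wrong on this point. If that sentence is right, the title misdescribes the cohort. The reader cannot tell which, and by the protocol's own account the answer matters for histologic regression.

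The trial has no concurrent control. The within-subject tests in 12.1 to 12.3 cannot separate a drug effect from spontaneous regression, which is at least 20-25% in this window. External comparison (this cohort in 12.4, the colposcopy database in 7.2) is the only planned check. A difference in genotype mix could be read as activity, or could hide it, and the Synopsis carries exploratory results with p of 0.10 or less forward for consideration in later trials.

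**Working it through.** The documents give no sample size, power or error rate for this comparison, so there is no planned figure to reproduce.

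**Inputs from the documents**
- HPV16 regression: 20-25% (5.0); midpoint 0.225 used.
- Non-HPV16 regression, q: higher than HPV16, no figure given (5.0).
- Cohort size: over 250 (12.4); 250 used.
- Test: 12.4 names none; the simple chi-square at p < 0.1 from 7.2 is used.
- Trial patients: 9 (one of cohorts II-IV), 21 (9 plus the 12 expansion patients in 12.1), or 27 (cohorts II-IV pooled).

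**Assumed, not in the documents:** trial HPV16 share s of 40-60%; q of 35-55%; the three groupings above.

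**Case 1: cohort HPV16-only, inert drug**

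Expected trial rate = s × 0.225 + (1 − s) × q.
Bias = (1 − s) × (q − 0.225). This is positive whenever q exceeds 0.225 and any non-HPV16 patient is enrolled.

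- Low: s = 0.6, q = 0.35: 0.135 + 0.140 = 0.275; bias +5.0 points.
- Middle: s = 0.5, q = 0.45: 0.1125 + 0.225 = 0.3375; bias +11.25 points.
- High: s = 0.4, q = 0.55: 0.090 + 0.330 = 0.420; bias +19.5 points.

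Probability of p < 0.1 in the drug's favour, by exact enumeration of the two binomials with the uncorrected chi-square:

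| Trial n | Genotypes matched | Low | High |
|---|---|---|---|
| 9 | 0.063 | 0.120 | 0.397 |
| 21 | 0.058 | 0.148 | 0.622 |
| 27 | 0.056 | 0.158 | 0.695 |

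Wider assumptions (s 30-70%, q 25-60%) give 0.070-0.555 at n = 9 and 0.067-0.880 at n = 27. A separate grid (HPV16 rate 0.20-0.25, q 0.30-0.50, s 40-60%, n = 30) gives a bias of +2 to +18 points and a probability of 0.088-0.696.

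**Case 2: cohort mixed, inert drug** (s = 0.5, q = 0.45, so trial rate 0.3375; n = 27)

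| Cohort HPV16 share | Cohort rate | Favours drug | Against drug |
|---|---|---|---|
| 80% | 0.270 | 0.193 | 0.009 |
| 60% | 0.315 | 0.084 | 0.028 |
| 50% | 0.3375 | 0.052 | 0.047 |
| 40% | 0.360 | 0.031 | 0.075 |
| 30% | 0.3825 | 0.018 | 0.114 |

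With a real gain of 22.5 points in both genotype groups (trial rate 0.5625), crude power at n = 27 is 74% with matched mixes, 66% at a 40% cohort share and 57% at 30%. An imbalance in this direction hides activity.

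The documents give no genotype direction for viral load, so none is claimed.

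**The case against.** The strongest reply is that the cohort may well be mixed. 12.4 says so in effect, 9.0 speaks of the same population, 8.0 names a CIN2/3 cohort without a genotype limit, and the title of a cited regression study mentions HPV type. A study title is not an eligibility criterion. On that reading the distortion is small when the HPV16 shares are close: at cohort shares of 40-60%, the favourable rate at n = 27 is 3-8%. This stands as a real possibility, but it does not settle the matter. 9.0 speaks of the studies collectively and is silent on genotype, and a mixed cohort still biases a crude comparison when its HPV16 share differs from the trial's.

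It is also fair that the probabilities stack several assumptions and borrow a test that 7.2 attaches to a differently named comparator. They show direction and possible scale, not an estimate. A purely descriptive comparison would carry the same bias in the point estimate.

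Finally, the consequence is limited: safety is the primary outcome, the analysis is mainly descriptive, and dose selection rests on within-subject change. Trial genotypes are collected, so stratification could be added later. That holds only if the cohort's genotypes are available too, and a choice made after seeing results is weaker than a prespecified one.

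**Conclusion.** The concern holds as a conditional statement. The cohort's title and the sentence on shared eligibility conflict, and no genotype handling is planned for a factor that the protocol itself calls prognostic. If the cohort is HPV16-only, the crude histologic-regression comparison favours the drug; this needs only 5.0's statement on other genotypes and some non-HPV16 patients in the trial. If it is mixed, the sign depends on whether its HPV16 share is above or below the trial's.

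The size is uncertain. Under the main assumptions, the chance of a spurious favourable result in the HPV16-only case is 12-40% for 9 patients and 16-70% for 27, against about 6% when genotypes match. The plan should be changed, but this does not threaten the trial's primary aim. Confidence is medium, because the cohort's actual criteria are not in the documents.

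**What to change.** - Reconcile the title with the eligibility sentence in 12.4: state the cohort's HPV criteria and its actual genotype mix.
- If the cohort is HPV16-only, compare HPV16+ trial patients with it and report the other trial patients descriptively.
- If it is mixed, stratify histologic regression by HPV16 status (Mantel-Haenszel).
- State in advance how co-infection with HPV16 and another type is classified.
- If cohort genotypes cannot be retrieved, show the rates side by side without a test and name genotype mix as a limitation.
- HPV16 status can reasonably enter the viral-load and lesion-size comparisons too, with no direction of bias claimed for viral load.

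**Cost.** The text change is short. It depends on retrieving cohort genotypes: the documents show genotyping for trial patients, and 8.0 says that the trial's assessments, virologic ones included, parallel those of a CIN2/3 cohort, which suggests but does not prove that the data exist.

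An HPV16-only comparison leaves about 11-16 of 27 patients (27 × 0.4 = 10.8; 27 × 0.6 = 16.2). Power for 45% against 22.5% at two-sided 0.10 is then 53-63%. With 27 HPV16+ patients it would be 79%, but a mixed trial does not have that many. For one cohort of 9, about 4-5 patients remain, with power of 25-39%, against 47% if all 9 were HPV16+.

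Stratification with a mixed cohort costs little. In simulation (100,000 runs per setting, trial HPV16 share 50%, cohort share 30-80%), Mantel-Haenszel without continuity correction keeps favourable false positives at 5-6%. Its power for a 22.5-point gain is about 75-76% at n = 27 and 42-43% at n = 9.

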**Statistical Analysis Plan** Statistical analysis will be primarily descriptive due to the small sample size. Treatment related safety and efficacy attributes will be analyzed using the Chi-square test. Any exploratory inferences with a p-value of  $\leq 0.10$  will be considered for further study in subsequent trials.

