A larger goal of these clinical trials is to correlate measures of immune response with known clinical parameters of disease. The larger implications of this effort lie in the identification of appropriate and relevant measures of the mucosal immune microenvironment. The identification of intermediate biomarkers in the tissue not only serves to further our understanding of the immune response and our efforts to manipulate it, but also has practical implications in the setting of monitoring patients at risk for disease recurrence or progression. In the case of high grade cervical intraepithelial neoplasia, lesion size and viral load are both quantifiable risk factors for persistent and progressive HPV disease. Therefore in these trials we will quantitate both outcome measures sequentially and correlate them with local tissue and peripheral measures of immune response.

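### The efficacy comparison with the external cohort is non-randomised and unadjusted, although the protocol names lesion size, viral load and HPV genotype as prognostic

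*Combined protocol and SAP*

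**What the plan says.** Section 12.4 sets up the external comparison: "The secondary efficacy endpoints will be compared with analogous data obtained in a currently open cohort study". It then states "We will compare changes in HPV viral load and lesion size from baseline at Week 15, rates of histologic regression", followed by change in viral load over the 15-week window, in both cohorts. No model, covariate, matching or weighting is named. The section supports comparability by stating that the cohort has the same eligibility criteria and the same follow-up window.

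The only test named for treated women against external data is in Section 7.2. Efficacy indicators there come from evidence "demonstrating a significant difference (by simple chi-square analysis" at p<0.1) "between treated subjects and the baseline data in the Johns Hopkins Colposcopy database". The synopsis agrees on the method: "Treatment related safety and efficacy attributes will be analyzed using the Chi-square test". It also says that exploratory inferences with p≤0.10 will be considered for later trials.

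On prognosis, Section 5.0 says that "lesion size and viral load are both quantifiable risk factors for persistent and progressive HPV disease". On genotype it says: "Lesions that are associated with HPV genotypes other than HPV16 are even more likely to regress in this timeframe". It gives a 15-week regression rate of about 20-25% for HPV16 lesions.

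On data, Section 8.0 says "These serial assessments will directly parallel those obtained in the currently open CIN2/3 cohort study". Section 12.4 plans changes from baseline in both groups, which implies that baseline viral load and lesion size exist in both.

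**The concern.** Without randomisation, a crude difference between trial and cohort mixes any drug effect with differences in who entered each study. Shared entry criteria limit who can join; they do not equalise lesion size or viral load among women with CIN2/3. The protocol says that these factors, and genotype, bear on the outcome being compared, but the stated comparison uses none of them as a covariate.

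Genotype is the one factor on which the documents themselves suggest a difference. Section 12.4 gives the cohort study a title restricted to HPV16+ lesions, while Section 9.1 requires only a positive HPV DNA test. That title does not sit easily with the statement, also in Section 12.4, that the eligibility criteria are the same.

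At stake is whether a result at p<0.1 against the cohort is read as drug activity and carried into the next trial, or whether real activity is missed.

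**Working it through.** **No plan figure to reproduce.** The documents give no effect size, SD, power or sample size for this comparison.

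**Inputs from the documents**
- Cohort regression 22.5%, the midpoint of 20-25% (Section 5.0).
- Cohort size 250 (Section 12.4: over 250).
- Treated at 200 mg: 9 + 9 + 9 = 27 (Table 4).
- Threshold p<0.1 (Section 7.2), taken as two-sided.

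**Assumed inputs, not in the documents**
- Odds ratio for regression of 0.5 to 0.7 per SD of a baseline factor.
- Baseline imbalance of 0.5 or 0.75 SD.
- Correlation rho of 0.3 to 0.7 between baseline and week 15, with equal SDs.
- Genotype mix and non-HPV16 regression rate as in step 2.

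**1. Histologic regression, inert drug.** Use logit(p) = a + ln(OR)·x, with x standard normal in the cohort and a chosen so that mean p = 22.5%. Then shift the trial mean of x.

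| OR per SD | 0.5 SD lower (favourable) | 0.75 SD lower | 0.5 SD higher (unfavourable) |
|---|---|---|---|
| 0.5 | 28.5% | 31.9% | 17.4% |
| 0.6 | 27.0% | 29.5% | 18.5% |
| 0.7 | 25.7% | 27.4% | 19.6% |

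A favourable 0.5 SD shift adds 3.2 to 6.0 points of false benefit. An unfavourable one hides 2.9 to 5.1 points. With 27 against 250, a simulated chi-square at 0.10 rejects in about 13-20% of trials for the favourable 0.5 SD shift, and in up to about 30% for 0.75 SD.

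**2. Genotype.** If a share s of trial women are non-HPV16 and regress at rate r, against 22.5% in an HPV16+ cohort, the spurious difference is s × (r − 22.5%).
- s = 0.3, r = 35%: 0.3 × 12.5 = 3.75 points.
- s = 0.5, r = 45%: 0.5 × 22.5 = 11.25 points.

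The range is about 4 to 11 points, at least as large as in step 1. Adjusting for lesion size and viral load alone would leave it in place.

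**3. Viral load and lesion size.** Under equal SDs, the variance of the baseline-adjusted estimate relative to the change score is (1 + rho)/2: 0.65, 0.75 and 0.85 for rho = 0.3, 0.5 and 0.7.

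For bias, let the groups differ by d at baseline and let the drug be inert.
- If both groups regress towards a common mean, the change score is biased by (1 − rho)d in absolute size. With d = 0.5 SD that is 0.35, 0.25 and 0.15 SD. Its standard error is √[2(1 − rho)] × √(1/27 + 1/250), which gives rejection rates of 43%, 34% and 25% at a nominal 10%.
- If the difference d is stable to week 15, the change score is unbiased. The adjusted estimate is then off by d − rho·d = (1 − rho)d, the same size.

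The data in hand cannot settle which case applies.

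**4. Precision for the binary endpoint.** In 1,500 simulated data sets (27 against 250, two covariates with assumed log-odds 0.6 per SD each), adjustment moved the SD of the risk difference from 0.084 to 0.079 with no imbalance, and from 0.0965 to 0.0953 with 0.5 SD imbalance in each. The SD of the log odds ratio rose, from 0.52 to 0.56 and from 0.47 to 0.52. With 0.5 SD imbalance in each covariate, rejection fell from 35% crude to 10.5% adjusted.

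**5. Events available.** 0.225 × 250 ≈ 56 regressions in the cohort and 0.225 × 27 ≈ 6 in the trial under no effect. That is enough for a few covariates with penalisation, but not many.

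**The case against.** The other side has substance. Safety is the primary outcome, the synopsis calls the analysis mainly descriptive, and Section 12.4 is headed exploratory. The expansion dose in Section 12.1 is chosen on within-subject viral load and lesion clearance, not on this comparison. Section 12.4 asserts the same eligibility and timeframe. These facts limit the stakes. They do not make a crude test the better choice when the covariates are at hand.

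Some stronger readings are tempting, but the documents do not support them.

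- **That the trial and cohort do differ in lesion size or viral load.** No baseline data are given for either group. This is a risk, and it can run in either direction.
- **That lesion size and viral load are the only prognostic factors named, or are said to drive persistence.** Section 5.0 calls them risk factors and also names genotype.
- **That baseline is ignored.** Viral load and lesion size are compared as changes from baseline, and a logistic model in Section 12.4 adjusts for baseline viral load. That model, however, relates viral load to regression. Neither it nor the random-effects model has a study-group term, so neither adjusts the comparison with the cohort.
- **That adjusting for baseline removes bias in the continuous outcomes.** Step 3 shows that it can equally introduce one if the groups differ stably.
- **That precision is lost throughout.** The gain is mainly for the continuous outcomes. For histologic regression it is small as a risk difference and reversed on the log-odds scale.

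**Conclusion.** The point holds as a gap in pre-specification. A non-randomised comparison that Section 7.2 treats as a source of efficacy evidence is planned with a crude test, while the protocol itself names three prognostic factors. For one of them, genotype, the documents suggest a difference between the groups.

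The true size is unknown. Under the stated assumptions, a 0.5 SD favourable imbalance in one factor would make an inert drug show about 26-29% regression against 22.5%, and the genotype mix could add about 4 to 11 points. Only the 20-25% regression rate, the group sizes and the p<0.1 threshold come from the documents. The change is worth making, but because the analysis is exploratory and secondary, it does not threaten the trial's primary purpose.

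**What to change.** Amend Sections 7.2 and 12.4 as follows.

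1. **Comparator.** State whether the colposcopy database in Section 7.2 and the cohort in Section 12.4 are the same source, and whether the cohort is restricted to HPV16+ women.
2. **Histologic regression.** Replace the crude chi-square as the main analysis with a penalised logistic model on study group, baseline lesion size, log10 baseline viral load and HPV16 status, reported as a standardised risk difference with a confidence interval.
3. **Genotype.** If the cohort is HPV16+ only, restrict the primary comparison to HPV16+ trial women. Non-HPV16 women would then have no cohort counterparts, and a covariate cannot supply them.
4. **Week-15 log viral load and lesion size.** Report a model on study group plus the baseline value next to the planned change-score comparison. Say that the two rest on different assumptions in non-randomised groups, and interpret with caution if they disagree.
5. **Crude results.** Report them alongside, with a baseline table for both groups.

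The cost is some analysis work on data that the protocol indicates both studies collect. Women missing a baseline value need imputation or drop out of the adjusted model, and the rule should be written down beforehand. Restriction to HPV16+ also costs numbers: if 30-50% of the 27 women at 200 mg were non-HPV16 (assumed), about 14 to 19 would remain.
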